Behavioral Sleep Interventions: A recent systematic review and meta-analysis found behavioral treatments for young, typically developing children (birth to 5 years) with sleep disturbances result in significant improvements in sleep-onset latency, night waking frequency, and night waking duration.⁶⁵ However, there is currently very low-quality evidence for behavioral treatments in adolescents, as well as children/adolescents with NDDs.⁶⁵ A few studies have shown that interventions predominantly aimed at parent education in pediatric sleep hygiene improve sleep disturbances in young children with NDDs,⁶⁶⁻⁷¹ as well as older children and adolescents with DDs.⁷² Currently, behavioral sleep interventions for children with NDDs are sparse and limited by methodological concerns (e.g. small sample sizes, wide age ranges, & lack of objective measures).^{6,12,65,73} To our knowledge, no studies have reported behavioral sleep interventions specific to adolescents with NDDs. Behavioral interventions and exogenous melatonin show promise in treating sleep problems in adolescents with NDDs.⁷⁴

CHARACTERISTICS OF THE SUBJECT POPULATION

4. Accrual

Is this study conducted solely at sites under the oversight of the Joint Pediatric IRB (e.g. UNMC, TNMC, CH&MC, UNO)?

Yes

A. What is the total number of subjects (per group, as applicable) needed to complete the research in order to achieve the scientific objectives of the research?

A convenience sample of 40 adolescents diagnosed with ASD and/or ADHD and 40 parents (or legal guardians) of adolescents (1 parent per adolescent) will be recruited through the UNMC MMI, all MMI outreach clinics, CHMC, and CHMC clinics. A focused plan will be in place to oversample females (e.g. clinicians and study team will be encouraged to invite non-white and female adolescents to participate), given the approximate 4:1 male to female ratio of NDDs. Our anticipated ratio is 3:1 male to female participants. Adolescents and their parent will be identified by a doctoral-prepared nurse as meeting the inclusion criteria.

B. What is the statistical or other justification for the total number of subjects needed to complete the research in order to achieve the scientific objectives of the research?
The sample of 40 was chosen following a sample size calculator, specific to pilot SMARTs,⁷⁵ assuming 85% probability, an estimated early non-response rate of 50%, and a minimum of 3 participants falling into the non-responder groups.

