C. Based on the anticipated number of screen failures and/or subject withdrawals, what is the maximum number of subjects that will need to be consented in order to achieve the scientific objectives of the research?

The maximum number of adolescent study participants with ASD and/or ADHD that will be consented is 40. In addition, a maximum of 40 parents of the adolescent participants will also be consented, for a total maximum number of 80 participants. [name] (PI) will meet participants in-person at baseline, week 4, and week 8. In addition, endogenous melatonin samples will be collected from participants by the end of the first week of baseline data collection. [name] will conduct weekly telephone check-ins to discuss daily adherence to the Bedtime Bank (e.g consistent bedtimes and tracker completion) and wearing the actigraph. Technical problems will be triaged quickly and may result in additional telephone calls or in home visits when necessary to further help with participant retention. Participants will also be compensated for their time.

5. Gender of the Subjects

A. Are there any enrollment restrictions based on gender?

No

6. Age Range of Subjects

A. What is the justification for inclusion of children in this research?

Adolescents (10-18 years of age) with neurodevelopmental disorders (NDDs) are included in this study. Adolescents with NDDs are vulnerable to sleep disturbances, and there is a critical need for evidence-based sleep interventions that target this population. The PI, mentoring team, and staff at the facilities in which the participants will be recruited all have expertise in accommodating for adolescents with NDDs. The proposed study will pilot a sequential, multiple assignment, randomized trial (SMART) design utilizing exogenous melatonin, The Bedtime Bank, and their combination for the management of sleep disturbance in adolescents with NDDs. Knowledge gained from this study will contribute to future full-scale SMARTs and our long-term goal of developing evidence-based guidelines for sleep interventions for children and adolescents currently experiencing or at-risk for sleep disturbances.

B. What is the age range for the child subjects, and what is the justification for selecting this age range?

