- 5) Medication-free or on a stable dose of medications (no changes within 30 days prior to enrollment) with parental agreement to avoid changes in current medications (unless provider directed) during study participation

Adult Inclusion Criteria:

- 1) Parent/guardian of an adolescent participant
- 2) Age 25-65 years and consistently living with the participating adolescent

10. Exclusion Criteria

What are the specific exclusion criteria?

Adolescent Exclusion Criteria:

- 1) Unwillingness to stop melatonin 2 months prior to enrollment in the study
- 2) Parent report of adolescent with a known sleep disorder (e.g. sleep apnea)
- 3) Adolescents who are not able to take oral medication
- 4) Adolescents who are visually impaired with known inability to detect light
- 5) Adolescents with an NDD with known genetic etiology (e.g. Angelman syndrome)
- 6) Unwillingness to wear actigraph daily and complete daily sleep diary throughout the 9-week trial

Adult Exclusion Criteria:

- 1) Unwillingness to wear actigraph daily and complete daily sleep diary throughout the 9-week trial

11. Pregnancy and Contraception Requirements

A. Are non-pregnant females of childbearing potential included in this research?

Yes

1) Are there any specific contraception requirements?

No

1) Provide justification.

No interventions are likely to be of risk to a fetus (including Category A drugs)

- ♦ Other. Explain. It is currently not known if there is any risk to the fetus from exogenous melatonin.

B. Are pregnant females included in this research?

No

1) Provide justification for excluding pregnant females.

Intervention includes a Category B, C, D or X drug

Intervention includes a procedure expected to be of risk to the fetus (e.g. exposure to ionizing radiation, maximal exercise test)

Research is not relevant to pregnant females (e.g. disease or condition rarely encountered in pregnant females)

Knowledge being sought in the research is already available for pregnant females or will be obtained from another ongoing study

A separate study in pregnant females is warranted and preferable

Physiology of pregnancy precludes generalization to other populations

- ♦ Other. Explain. Pregnant females may have different sleep patterns potentially confounding the study interventions.

2) Describe how pregnancy status will be assessed.

♦ Self-report

Blood pregnancy test

Urine pregnancy test

N/A study includes males only

C. Are breast feeding females excluded from participation?

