metabolite in urine, correlates well with the total level of melatonin in the blood during the collection period.⁸⁵ At baseline, adolescents and parent(s) will be given the urine collection kit and instructed on how to collect the adolescents urine (first morning void and evening), including written instructions (Appendix L) and a mock return demonstration. The pre-labeled and de-identified urine samples will be collected from participants by responsible personnel prior to the implementation of the first stage intervention. Specimens will then be stored in a locked and secured freezer (at the UNMC Biospecimen Bank) until they can be run by the UNMC Biospecimen Bank staff for analysis. Urinary creatinine will also be measured as melatonin sulfate is referenced as ng/mg creatinine to control for dilution of urine. Urine samples will only be used for the study described in the consent form.

3. Actigraphy: Objective measure of sleep patterns based on the correlation between sleep-wake state and motor activity. Adolescents wear the Actiwatch Spectrum (Philips Respironics, Bend, OR) on their wrist for 7-days (24 hrs/day) to establish baseline sleep patterns, as well as for 4 weeks (24 hrs/day) for the first stage treatment. TST will be used as the primary tailoring variable to determine responder status. A minimum of 4 weekday nights (Mon-Thurs) and 1 weekend (Fri-Sat) night is required. Participants will be provided with information regarding the care and use of the Actiwatch (Appendix M).
4. Sleep Diary: During the time adolescents are wearing the actigraph, adolescents will record an approximate time of sleep and wake to aid in data analyses.⁸⁶ Participants will also be asked to write down any times the device is removed, prolonged quiet activities, and atypical sleep (Appendix C). Reliability in completing the diaries will be established via weekly telephone checks by the study's investigators.
5. MEMs Button: Medication adherence will be monitored using MEMs Buttons. This button is attached to the melatonin bottle. When a dose is administered, the adolescent or parent will press the button to record the dose. Data from the MEMs Button will be downloaded from the device to a computer to ensure dose fidelity.
6. First Stage Treatment (see **Figure 2**): Adolescents will be randomly assigned to 4 weeks melatonin OR 4 weeks of *The Bedtime Bank*. Randomization will follow the real-time randomization for SMART designs.⁷⁵

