Monitoring study safety will occur from the initial screening, throughout the informed consent process, and through study completion. Weekly monitoring of participants (telephone check-in) and internal monthly quality audits of protocol fidelity will occur. Any adverse events will be reviewed in real time according to University policy. Follow-up visits to analyze and discuss treatment acceptability will be scheduled every four weeks throughout the eight-week study, for a total of three visits. During this time, any stress or discomfort encountered as a result of the study will be discussed. The PI and study coordinators will also be available to the study participants via phone or email should the participants or their parents have any questions or concerns regarding the study.

C. Describe the process by which the PI will be informed and how the PI, in turn, will inform other research staff about events concerning subject safety (including (a) interim results; (b) adverse events; (c) unanticipated problems involving risks to subjects or others; (d) noncompliance; (e) complaints).

1) At UNMC/TNMC/CH&MC and/or UNO (check all that apply).

Not applicable. The PI is the only person listed in Section I of the IRB Application.

♦ By email or campus mail (for events which do not constitute immediate subject safety hazards)

♦ By phone

♦ By in-person meeting

By scheduled submission of case report forms

Other. Explain.

2) At external study sites under the oversight of the Joint Pediatric IRB as applicable

(check all that apply).

By email or mail (for events which do not constitute immediate subject safety hazards)

By phone

By in-person meeting or teleconference

By scheduled submission of case report forms

♦ Other. Explain. N/A

D. Describe the auditing plan for research conducted:

1) Within the Organization (UNMC, TNMC, UNO or CH&MC), identify who will conduct the audits and specify the audit frequency.

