The investigators will withdraw individual subjects from the research if they no longer meet inclusion/exclusion criteria. Individual subjects will also be withdrawn from the research by investigators if the participating adolescent or his/her parent(s) withdraws consent to participate at any time.

G. Describe the specific criteria for halting or early termination of the study (for example statistical evidence of unacceptable toxicity or early demonstration of efficacy or lack of efficacy).

Monitoring study safety will occur from the initial screening, throughout the informed consent process, and through study completion. Weekly monitoring of participants (telephone check-in) and internal monthly quality audits of protocol fidelity will occur. Any adverse events will be reviewed in real time according to University policy. The research will be terminated if, for any reason, it appears that the participants are at risk. The research will also be terminated if the parent of the participant (or the participant him/herself) expresses desire to discontinue to the investigator.

H. Describe plans and resources available to promptly address any subject injury.

[name] (PI) will be responsible for ensuring that all adverse events and unanticipated problems are reported to the senior nursing scientist assigned as co-mentor ([name]), the University of Nebraska Medical Center Institutional Review Board, and the NIH. Per University policy, all serious adverse events (AE) will be reported to the UNMC IRB within two business days after the PI is notified of the AE. Any fatal adverse events will be reported immediately according to institutional policies.

19. Potential Benefits to the Subject

Are there potential benefits to the subjects that may reasonably be expected from participation in the research?

Yes

Describe.

This study has the potential to increase total sleep time in adolescent participants. This study could have positive effects on the adolescent's sleep habits, as well as his or her family's quality of life.

20. Potential Benefits to Society

What are the anticipated benefits (i.e., value) to society that may reasonably be expected to result from this research?

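### Read literally with exclusion 6, the withdrawal rule in Section 18.F ends follow-up for a still-consenting adolescent who stops the actigraph or diary, and no visible text keeps the later acceptability assessments

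*Combined protocol and SAP*

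**What the plan says.** Section 18.F gives two routes by which the investigators remove a subject. The first is eligibility: "The investigators will withdraw individual subjects from the research if they no longer meet inclusion/exclusion criteria". The second, in the next sentence, is withdrawal of consent by the adolescent or parent.

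Adolescent exclusion 6 in Section 10 reads "Unwillingness to wear actigraph daily and complete daily sleep diary throughout the 9-week trial".

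Section 12.B and Table 1 schedule the AARP, CASQ and PROMIS questionnaires and a semi-structured interview at Week 4 and again at Week 8. Section 18.B describes the purpose of these contacts: "Follow-up visits to analyze and discuss treatment acceptability will be scheduled every four weeks throughout the eight-week study", and "During this time, any stress or discomfort encountered as a result of the study will be discussed". Section 12.F names feasibility and acceptability as what the pilot will address, with acceptability measured by the AARP and the interview.

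Other text is more tolerant of incomplete participation. The investigator "will conduct weekly telephone check-ins to discuss daily adherence to the Bedtime Bank (e.g consistent bedtimes and tracker completion) and wearing the actigraph" (Section 4.C). For actigraphy, "A minimum of 4 weekday nights (Mon-Thurs) and 1 weekend (Fri-Sat) night is required" (Section 12.B). At Week 4, item 7 of Section 12.B lets adolescents who do not complete their assigned treatment either stay on it or leave the study.

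**The concern.** The first sentence of 18.F is mandatory, speaks of removal from the research rather than from treatment, and refers to criteria that are no longer met, which points to a change after enrollment. Exclusion 6 describes a state that can arise during the trial. An adolescent who tires of 24-hour wear or of the daily diary, but whose family is content to go on with the rest, then falls under the rule.

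What would be lost is information the pilot exists to collect. A family that finds nine weeks of monitoring unworkable can say something useful about the design of the full-scale trial. The AARP, questionnaires and interview can all be completed without an actigraph. Because the family still consents, the loss is avoidable.

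**Working it through.** No figure in the plan is disputed. The check is mainly a comparison of texts, followed by simple arithmetic on loss and cost.

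**Does the rule reach this adolescent?**

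1. Section 18.F lists withdrawal of consent as an additional ground, so its first sentence covers subjects who still consent.
2. Criteria tied to the period before enrollment, such as stopping melatonin two months earlier, cannot lapse later. Exclusion 6 covers the whole 9 weeks, so it can.
3. The trigger is unwillingness, not missed nights. Wear is followed up by weekly calls, a minimum number of nights is set, and the answer to 18.F does not take up the form's own example of non-compliance.

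**Does any visible text keep the later assessments?**

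- Section 4.C: calls and home visits to support retention, before any withdrawal.
- Section 12.B, Week 4 item 7: concerns not completing treatment, not stopping the device or diary.
- Section 12.F: missing data is named as a feasibility topic, with no rule for handling it.
- Section 16: answers discomfort with the device by the right to withdraw from the research.
- Section 18.D: withdrawals are reported to the DSMB, with no later assessment.

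None of these provides for the Week 4 or Week 8 assessments after removal under 18.F.

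**Loss per affected family.** Post-baseline sets scheduled = 2 (Week 4 and Week 8).

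- Stopping before Week 4: 2/2 = 100% lost.
- Stopping between Weeks 4 and 8: 1/2 = 50% lost.

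**Cost of keeping the assessments.** Times are from Table 1, added as if done one after another.

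- One visit: AARP 5-7 + CASQ/PROMIS 7-11 + interview 10-12 = 22-30 minutes.
- Two visits: 2 x 22 = 44 to 2 x 30 = 60 minutes.
- Payment (Section 23): the plan's total of 3 x $40 = $120 is reproduced. One retained visit is $40 and two are $80, both inside that total.

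**The case against.** The strongest reply is that the event is inferred. No single sentence says that refusing the actigraph leads to removal. Exclusion 6 sits among the enrollment criteria and can be read as a question put at screening about what the family will agree to. The ongoing reading also proves too much: applied to inclusion 4 (short time in bed or a high sleep-habits score), it could remove an adolescent whose sleep improves, although Section 12.B keeps responders on their treatment. Section 16 presents device discomfort as a matter for the family's own choice. All of this stands as evidence that the clause may have been meant only for subjects found ineligible. It does not remove the difficulty, because the text as written does not say so.

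Several stronger readings are tempting, and the documents do not support them:

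- **That missed nights lead to withdrawal.** The adherence calls and the minimum-nights rule point the other way.
- **That acceptability results will be biased in a known direction.** The AARP rates the treatment, and its visible description has no item on the device.
- **That discomfort would go unrecorded.** Section 18.B also provides weekly calls, real-time review of adverse events, and phone or email contact. What is lost is the account at the scheduled visit.
- **That the loss undermines the sample size.** Section 4.A plans "A convenience sample of 40 adolescents diagnosed with ASD and/or ADHD", and Section 4.C says "The maximum number of adolescent study participants with ASD and/or ADHD that will be consented is 40", so spare consents are 40 - 40 = 0. But Section 4.B sizes the 40 to give at least 3 participants in the non-responder groups. Retaining adolescents who have no response status would not restore those groups.
- **That no provision exists anywhere.** The consent pages and the separate data and safety monitoring plan are not available here and could contain one.

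**Conclusion.** The concern holds in a limited form. Taken literally, 18.F and exclusion 6 end follow-up for an adolescent who stops the actigraph or diary but still consents to the rest, and no visible text preserves the later AARP, questionnaires and interview. Families who withdraw consent are outside this point.

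It is minor. The number affected cannot be derived and is probably small, and neither the direction nor the size of any bias can be stated. The 100% and 50% figures describe one affected family, not the trial. The conclusion rests on combining two clauses and on the absence of a provision in the text that can be seen. Confidence is medium. It merits a change because a stated rule, if followed, discards acceptability data that consenting families could supply at little cost.

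**What to change.** Leave the other grounds in 18.F as they are; a sleep disorder that becomes known during the trial, for example, remains a sensible reason to withdraw a subject. Add three statements:

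1. Inclusion 4 and exclusion 6 are judged at enrollment only.
2. Stopping the actigraph or the diary is not by itself a reason for withdrawal from the research.
3. Unless consent is withdrawn, the Week 4 and Week 8 AARP, CASQ/PROMIS, interview and any available actigraphy are collected from all randomized adolescents.

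If the consent form or monitoring plan already says this, a cross-reference in 18.F is enough.

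The cost is protocol wording plus, per affected family, 22-30 minutes and an already planned $40 for each visit kept. The downside is that some retained adolescents will have no actigraphy-based response status and cannot be assigned a second stage by the responder rule. They could stay on their assigned treatment, as Section 12.B already allows for non-completers, or stop it and be followed for assessments only. That choice belongs to the investigators.

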For studies conducted at CH&MC: UNMC Disclosure of Potential Conflict of Interest Form for any responsible personnel with a financial interest declared in Section I.10.

- ♦ Other Appendix G, I, K, L, P, C, E, J, M, N,O

No attachments

ADDITIONAL REVIEW REQUIREMENTS

Final IRB approval and release of studies is contingent upon approval by the following UNMC committees or departments. Check the appropriate boxes:

Pharmacy and Therapeutics (P&T) Committee: Review by the P&T Committee is required for all protocols involving the use of investigational or marketed drugs.

UNMC Eppley Cancer Center Scientific Review Committee (SRC): Review by the SRC is required for all protocols involving cancer patients.

Institutional Biosafety Committee (IBC): Review by the IBC is required for all protocols involving the use of gene transfer and vaccines.

Radioactive Drug Research Committee (RDRC): Review by the RDRC is required for all protocols involving the use of a radio-labeled drug for which the investigator or the institution holds the IND.

Sponsored Programs Administration (SPA)/Office of Regulatory Affairs: For commercial sponsored studies, the consent form and contract will be compared for consistency by the ORA. Final IRB approval and release is contingent upon completion of a signed contract, verified by SPA, for all commercially sponsored research.

Conflict of Interest Committee (COIC): All responsible personnel listed in I.3A-E of the IRB application (i.e., PI, Secondary Investigator, Participating Personnel, and Coordinator(s)) must disclose **any** financial interest in the research (see Section I.10 of this application). Data and Administrative Personnel are exempt. The COIC will review any financial interest which is classified as significant.

Investigational Device Review Committee (IDRC): Review by the IDRC is required for all protocols involving the use of investigational or marketed devices.

Other Review

- ♦ **No Additional Reviews Required**

ADDENDUM Q
Investigational New Drugs or Biologic Drugs

Title of Protocol

A SMART Design to Improve Sleep Disturbance in Adolescents with Neurodevelopmental Disorders

Principal Investigator

[name] - CON-Omaha Division - [contact] - [contact]

A. Investigational New Drugs and Biologic Drugs

1. Does this research involve an investigational drug or biologic drug?

No

B. Investigations Using FDA-Approved and Marketed Drugs or Biologic Drugs

1. Does this research involve an investigational use of an FDA-approved and marketed drug or biologic drug?

No

ADDENDUM Y

Research Involving Adults as Subjects Participating in a Pediatric Trial

Title of Protocol

A SMART Design to Improve Sleep Disturbance in Adolescents with Neurodevelopmental Disorders

Principal Investigator

[name] - CON-Omaha Division - [contact] - [contact]

Waiver of Alteration of Informed Consent

Is a waiver of alteration of consent requested?

No

1. Capacity to Consent

a. At the time of initial consent, will all subjects have the capacity to give informed consent?

Yes

b. Is there a reasonable likelihood that some subjects may lose the capacity to continue to provide informed consent during the course of the study?

No

2. Process of Informed Consent for Competent Adult Subjects

a. When will the prospective subject be approached relative to their actual participation in the study?

Parent(s) of the children will be approached first to determine their interest. If the parent expresses further interest in participating in the study, the investigator will set up a date and time convenient to the parent to meet one-on-one at UNMC, MMI, CHMC, or to converse over the phone to further explain the study.

b. What is the location where informed consent will be obtained, and how will the environment be conducive to discussion and thoughtful consideration?

Informed consent will be obtained in a private room located XXX. This is a convenient location and will provide parent(s) the opportunity to ask questions in a private setting.

c. Who will be involved in the process of consent and what are their responsibilities?

The principal investigator ([name]) or study coordinators ([name] and [name]) will be involved in the consent process, including explanation of the

research, training procedures, and participant question/concerns.

d. How much time will be allotted to the process of consent?

The parent(s) will be scheduled for a meeting within two weeks of their expressed interest in study participation. The consent process is anticipated to take approximately 10 minutes, but an additional 20 minutes will be allotted to allow time for participant questions (total of 30 minutes allotted).

e. How will the process of consent be structured for subjects who are likely to be more vulnerable to coercion or undue influence?

Both the primary investigator and study coordinators have completed CITI training and are aware of the ethical considerations in obtaining informed consent. Additional protections during the consent process may include a subject advocate, involvement of subject's family or friends, use of teaching aids, and allotment of ample time for questions or concerns.

f. Will non-English speaking subjects be enrolled in this research?

No

Provide justification for why non-English speaking subjects will be excluded.

Non-English speaking subjects will not be recruited at this time because the Bedtime Bank is currently developed in English.

g. How will it be determined that the subject understood the information presented?

Parents will be given a flier along with the consent form, and they will have an opportunity to meet with the principal investigator or study coordinators to further review the study information. Parents will also be provided with contact phone numbers should they have any further questions or concerns. Parents will be asked to paraphrase the nature of the research, methods, and study risks and benefits, as well as that participation is voluntary.

h. Will there be a formal process of *on-going* re-consent (over and above re-consent associated with changes in protocol)?

No

3. Consent and Assent Forms

Indicate the type of consent forms and/or study information sheets to be used in this research:

♦ Adult consent form

Legally authorized representative (LAR) consent form

Adult study information sheet

Screening consent form
Addendum consent form
♦ Other. Explain. Adolescent Assent Form
